### **6.2.3 Data Collected**

A. Clinician Survey (Appendix A): Each clinician in the practice who will be participating in the study will be asked to complete a 10 minute survey about their knowledge of and current practices related to tobacco and nicotine product screening and interventions with their patients. These data will be collected at baseline and at 3 months post the intervention (9 months).

B. Practice Characteristic Data (Appendix B): The Change Process Capability Questionnaire (CPCQ) will be administered to all participating practices at the beginning and end of the study (baseline and 9 months). The CPCQ is designed to assess three domains: (1) the practices' history of change; (2) capacity for internal improvement and refinement; and (3) capacity to initiate and sustain change. Managing change is a key component necessary to adopt evidence-based best practices and the CPCQ provides valuable information about this dimension. Practices also will be asked to complete Adaptive Reserve Questionnaire (short form) at baseline and 9 months. This Survey was used in a National Institutes of Health (NIH)-funded study focused on deploying a health information technology (HIT)-enabled intervention to facilitate medical record reviews in primary care practices. The questions are designed to assess: (1) physician self-efficacy (current practices, comfort with, beliefs about, and barriers toward tobacco screening and counseling); and (2) the organizational structure available to support the implementation of new interventions such as the 6As intervention. This survey also will be administered at baseline and the end of the intervention period. The Medical Director for the practice will be asked to complete both surveys. This individual can ask for assistance from the Office/Practice Manager but most of the questions require a physician who is knowledgeable about the practice to complete the survey. Both surveys will take approximately 20 to 30 minutes to complete..

C. Youth Tobacco and Nicotine Product Questionnaire (Y-TNPQ) (Appendix C): At baseline, approximately 190 patients per practice in the intervention groups will be asked to complete a set of tobacco/nicotine product use questions while waiting for their clinician visit (either in the waiting room or another area designated by the practice without the parent being present). The questions were taken from the National Youth Tobacco Survey, a national survey designed to measure middle and high school youth's attitudes toward and behaviors related to tobacco and nicotine products.

The TNPQ will be administered using the ResearchACTS software. This software was used in an NIH-funded adolescent health risk assessment pilot project, and also in a Centers for Medicare and Medicaid Services-funded pragmatic clinical trial focused on cardiovascular disease risk reduction among Medicaid enrollees with multiple chronic conditions. ResearchACTS is a powerful, web-based application platform that is optimized for the iPad and collects, summarizes and tracks patient-reported information and can support cross-sectional and longitudinal studies with real-time data access for providers and researchers. Embedded within the application's functionality are regulatory and data quality safeguards to ensure the proper collection of high quality data that can be used by patients, providers, community members, and researchers in real time and support both quality improvement initiatives and pragmatic trials research. A distinctive feature within ResearchACTS is the ability to incorporate summary points of patient-reported data within the workflow

parameters. ResearchACTS software was developed at the University of Florida and all data collected is stored within UF's security environment.

The TNPQ will be programmed into ResearchACTS for the adolescent to answer. The clinician will then log into ResearchACTS and review the child's responses at the point of care. ResearchACTS contains motivational interviewing prompts to guide the clinician through the 6As (as appropriate for the child's responses).

D. Parent Brief Questionnaire (PBQ – Appendix D): The PBQ was developed using questions recommended by the American Academy of Pediatrics. Parents are one of the most important sources of a child's tobacco smoke exposure. Therefore screening parents is a recommended best practice. The PBQ will also be administered using ResearchACTS.

E. 6As and Best Practices Medical Record Review Form (6As MRR - Appendix E): At baseline, we will request the (Medical Record Number) MRN from the Integrated Data Repository (IDR) for 75 randomly selected patients from both control and intervention practices in Gainesville and Jacksonville, which will be reviewed for 1) adherence to the 6As (through whichever number of steps are applicable for that patient) inclusive of tobacco and nicotine product use and 2) parental screening for tobacco use. Specifically, the IDR will be asked to select MRNs from 75 records consecutively from well care visits from participating providers for patients 11 through 17 years of age from the 6 months prior to the start of the study until they reach 75 records. OneFlorida has a medical record review team with certified medical record coders. The medical record review team will measure compliance with the 6As and parental screening using the review tool. At the end of the intervention period, we will request the medical records for those patients participating in the intervention. We will request MRNs from the IDR for control group practices and review 75 consecutive medical records for patients ages 11 through 17 years seen during the 6 month study period.

[name] will train the medical record reviewers for the Gainesville and Jacksonville sites. Interrater reliability will be established and training will continue until there is 98% agreement between reviewers. During the record review process, [name] will be available to the reviewers to respond to questions. If there is not 98% agreement among the medical record reviewer findings, the medical record reviewers will undergo additional training from [name]..

For the medical record review for the UF sites (Gainesville and Jacksonville), certified medical record coders will access Epic, the electronic health record, directly if permission is granted from UF Health to do so. If permission is not granted, the clinic staff will be asked to provide PDFs of the children's records for the selected date ranges for the medical record reviewers to review onsite in the clinics. The 6As and Best Practices Medical Record Review Form (6As MRR - Appendix E) will be stored in UF REDCap.

F. Youth Tobacco and Nicotine Product Primary Care Questionnaire (YTNP-PCQ) (Appendix F): At 30 days post primary care visit, children with parental consent and their assent will be contacted via telephone to complete a 10 minute survey about their recollection of the tobacco and nicotine product discussions held with the clinician during the primary care visit. The YTNP-PCQ is adapted from the questionnaire used in the Adolescent Health Risk Assessment in Primary Care Study.

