## 6.2 Methods

### 6.2.1 Study Design

This study will be implemented with a convenience sample of 4 pediatric primary care practices. Two will be randomly assigned to receive the intervention and two will serve as the comparison groups. Two of the practices will be located at UF Health in Gainesville and two will be located at UF Health in Jacksonville. The control group will provide their usual care related to tobacco and nicotine product use screening and cessation recommendations. The control group will be given the opportunity to participate in the intervention following study completion.

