Practices will be asked to identify a location in the waiting room or an exam room where the screening tool can be completed without the parent present. Completing the tool is expected to take 10 minutes of the youth's time and 10 minutes of the parent's time, inclusive of the time to complete the informed consent. We estimate practices will need to participate in the project for approximately 6 months. This time period includes baseline and follow-up data collection, study implementation, and participant accrual. The 6-month time period is also necessary for those practices who wish to use the project for participation in their Maintenance of Certification (MOC) requirements.

The total duration of study participation for the practices is estimated to be 10 months. This includes a 3-month start up period, a 6-month intervention (or control) time period and a 1-month follow-up. The 6-month intervention period is necessary for those practices who want to use the study participation to assist them in meeting their MOC requirements. For practices not participating in the MOC Program, the intervention period is finished when 20 patients complete at least the “advise” and “assess” components.

Practices can make some modifications to the intervention to fit with their workflow. For example, some practices have nursing staff screen for tobacco/nicotine use and make recommendations about cessation strategies. Other practices have physicians provide the screening and counseling. Practices can make adaptations regarding who administers the 6As but they must follow the 6A intervention. Any type of primary care visit can be used to conduct the 6As.

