#### **6.2.4 Intervention**

Figure 2 shows a summary of the overall study and intervention. The following steps will be used to implement the intervention:

1. **Baseline Data:** Intervention and control practices will complete the Clinician and Practice Surveys and participate in the medical record review. They also will be asked to provide copies of any youth and parent health risk assessment or screening tools used in their practices related to tobacco and nicotine products.

2. Tobacco and Nicotine Product Screening: The intervention practices will receive the implementation supports listed in Figure 2. Intervention practices can make modifications to the study protocol to fit with their workflow, while maintaining the scientific integrity of the study. The steps for administering the TPNQ and Parent Brief Questionnaire (PBQ) using the ResearchACTS software at the point of care was described in the preceding *Data Collection* Section. As previously noted, the intervention is focused on the practice and not on the youth or the parents per se. Future studies will explore options related to implementing interventions and supports for youth related to tobacco and nicotine product cessation.
3. The control sites will deliver their usual care.
4. Upon study completion, implementation and control sites will complete the Clinician and Practice Surveys, participate in the medical record review, and have child reported outcomes results.

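### The plan does not fix the clinician list or the baseline surveys before practices learn their arm, and control follow-up charts are not limited to the providers sampled at baseline

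*Combined protocol and SAP*

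**What the plan says.** Section 6.2.1 randomises practices: "Two will be randomly assigned to receive the intervention and two will serve as the comparison groups". It gives no time for the allocation or for telling the practices.

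Section 6.2.3 A defines who answers the clinician survey: "Each clinician in the practice who will be participating in the study will be asked to complete a 10 minute survey". The survey is repeated at 9 months. Section 6.2.3 B has the Medical Director complete the practice surveys, and the introduction to Appendix A asks for one Appendix B per practice.

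Section 6.2.3 E uses the same undefined group for the baseline charts. The instruction for the data repository reads: "select MRNs from 75 records consecutively from well care visits from participating providers for patients 11 through 17 years of age". These visits all fall in the half-year before the study starts. At follow-up, intervention charts are those of patients who took part. For control practices the plan is to "review 75 consecutive medical records for patients ages 11 through 17 years seen during the 6 month study period".

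Section 6.2.4, step 1, describes baseline as follows: "Intervention and control practices will complete the Clinician and Practice Surveys and participate in the medical record review". Figure 2 likewise shows baseline under columns already headed by arm. It lists MOC support as part of the intervention, and for control practices only after the study.

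**The concern.** Two samples rest on the words participating clinician: the people surveyed and the providers whose baseline charts are read. The protocol does not say how a clinician joins, who lists them, or when the list closes. If practices already know their arm, joining means different things. In an intervention practice it brings facilitators, electronic prompts and MOC support during the study. In a control practice it brings usual care plus data collection, with MOC support and the chance to receive the intervention later. The clinicians who join could then differ by arm.

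The answers could differ too. Appendix A asks clinicians how often they ask, advise and refer, and such self-report can move once a clinician knows what the practice is about to do. With two practices per arm, a shift of this kind could not be told apart from chance imbalance between practices, and it cannot be repaired after the baseline is collected.

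The chart plan raises a related problem that does not depend on disclosure. In the control practices, baseline charts come from one set of providers and follow-up charts possibly from a wider one.

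**Working it through.** The plan states no figure on this point, so the check sets the sections side by side. The arithmetic is illustrative only.

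**1. Order of events.**
- Allocation: Section 6.2.1, no time given.
- Disclosure of the arm: not mentioned.
- Listing of clinicians: not mentioned.
- Baseline surveys: Section 6.2.4 step 1 and the first row of Figure 2, so before the intervention is delivered; not placed relative to allocation.
- Available time: Section 6.2.2 says of practice participation, "This includes a 3-month start up period, a 6-month intervention (or control) time period and a 1-month follow-up". None of the events above is placed within the start-up.

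Baseline therefore precedes the intervention, but need not precede knowledge of the arm.

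**2. What allocation could affect.**

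| Source | Who is sampled | Content |
|---|---|---|
| Clinician survey (Appendix A) | Yes | Yes, self-report |
| Practice surveys (Appendix B) | No, Medical Director | Yes, self-report |
| Baseline charts | Yes, through the choice of providers | No, visits precede the study |

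**3. Where baseline enters the analysis (Section 6.2.5).** The primary logistic model uses the pre-intervention measure as a covariate and in an interaction with group. Practice characteristics, measured at baseline and 9 months, are analysed by ANCOVA. No model is given for the clinician survey.

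**4. Size of a between-arm shift at baseline.** Let a share f of clinicians join, and let willingness to join correlate r with baseline practice (normal model). Joiners' mean then differs from that of all clinicians by r × φ(z(1−f)) / f standard deviations (SD). The between-arm shift is this quantity in one arm minus the same quantity in the other. The documents give neither f nor r. If joining depends on baseline practice in one arm only:

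| f | r = 0 | r = 0.3 | r = 0.5 |
|---|---|---|---|
| 0.9 | 0 | 0.06 | 0.10 |
| 0.7 | 0 | 0.15 | 0.25 |
| 0.5 | 0 | 0.24 | 0.40 |

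For example, at f = 0.5 and r = 0.3: 0.3 × 0.399 / 0.5 = 0.24. If f and r are the same in both arms, the shift is zero.

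**5. Control charts, before and after.** Let s be the share of eligible control visits seen by participating providers, and d their documentation rate minus that of the other providers. If care does not change and follow-up charts come from all providers, the apparent change is −(1 − s) × d. It is zero if s = 1 or d = 0. With assumed values s = 0.5 and d = 10 to 20 points, it is −0.5 × 10 to −0.5 × 20, that is, −5 to −10 points. With s = 0.9 it is −1 to −2 points. If the other providers document better, the sign reverses. This is an artefact within the control arm that needs no knowledge of allocation.

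**The case against.** The strongest reply is that this is silence, not a stated flaw. Protocols use arm labels for every step, so calling practices intervention or control at baseline does not show that they already know their arm. Baseline is listed first, and the 3-month start-up leaves room to complete it before disclosure. This stands: the documents support may, not will. A reader might infer that arms are disclosed first, or that different clinicians will volunteer and the balance from randomisation is lost. The documents say neither.

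Nor do they say that clinicians opt in one by one. The survey letter says that the practice agreed to take part, and its statement that participation is voluntary is addressed to the Medical Director or Office Manager. Individual choice is plausible but inferred. The contrast in incentives is also partly one of timing, since controls are offered the intervention and MOC support afterwards.

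A reader might also conclude that every Aim 2 comparison adjusts for a biased baseline. That goes too far: allocation cannot change the content of pre-study charts, clinician volunteering does not decide who answers for the practice, and no adjustment is specified for the clinician survey.

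Finally, a reader might assume that half the clinicians join and are 10 to 20 points better, and take the resulting 5 to 10 points as bias between arms. That figure is the gap between volunteers and all clinicians within one practice. It cancels between arms if selection is equal, and a volunteer list closed before allocation would leave it in place. It says nothing about a difference between arms.

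None of this answers the gap in the order of steps, or the different provider limits on the two sets of control charts.

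**Conclusion.** The concern holds as an omission with limited reach. The plan does not place the listing of clinicians or the baseline surveys before practices learn their arm. The clinician survey is exposed in who answers and how; the practice surveys only in how the Medical Director answers; the primary outcome only through which providers' pre-study charts are sampled. In addition, the stated chart rules allow the control pre-post comparison to rest on different clinicians.

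The size of either effect cannot be computed from the documents. The between-arm shift may be zero; the illustrative values above rest on an assumed share joining, an assumed correlation and selection in one arm only. If the sponsor already intends baseline before disclosure, one sentence settles the first part. The chart rule needs its own correction in any case.

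**What to change.** State in Sections 6.2.1 and 6.2.4 that, before the allocation is disclosed, all four practices list their participating clinicians and complete the Appendix A and B baseline surveys. In Section 6.2.3, draw the baseline charts and the control follow-up charts from that same list, and send the 9-month clinician survey to it. Report the number of eligible and participating clinicians in each practice, so that differential joining can be seen.

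The intervention-arm follow-up charts can stay as planned, limited to patients who took part; nothing here requires further record review.

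The cost is small: a re-ordering within the existing 3-month start-up, a provider filter on the control chart request, and a count of clinicians per practice. It must be done before practices are told their arm, because a baseline taken afterwards cannot be recovered.

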Despite national recommendations, compliance with the 6As and other PCP office-based best practices are low. The majority of pediatricians advise patients who smoke to quit (81%) but only one-third discuss cessation strategies, and less than 20% make referrals to the quitline or other cessation programs. Facilitators to carrying out the 6As and other best practices in primary care include: incorporation of cues into electronic health records (EHRs); use of short screening tools to identify those at risk for initiating tobacco use as well as current tobacco users; development of patient registries to track outcomes and to facilitate implementation of mHealth applications focused on tobacco cessation; and training of clinicians and office staff on cessation counseling.

The primary purpose of our study is to conduct a pilot, practice-based intervention focused on increasing adherence to the 6As for youth ages 11 through 17 years. We also will incorporate AAP best practice recommendations to screen and counsel parents.

Secondarily, we want to better understand the effects of the practice intervention on enhancing practice capacity to adopt and sustain new interventions in the future. The systematic uptake of evidence-based practices (EBP) into primary care is influenced by multiple organizational characteristics including practice leadership, ability to adopt new interventions (capacity for change) and sustain them (adaptive reserve); HIT availability, and clinician self-efficacy around the particular EBP. Therefore, we will measure practice characteristics including practice capacity for change, adaptive reserve, and HIT capabilities and clinician self-efficacy around the 6As at baseline and at 3 months post intervention.

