## 5. Specific Aims:

**Aim 1:** Develop and deploy an electronic short screening tool for tobacco and nicotine product use into pediatric primary care workflow in conjunction with 1) clinician and office staff training on the 6As and parent screening through the use of trained Clinical Practice Facilitators (CPFs), 2) clinician-engaged adaptations of the intervention to fit their practice workflow, and 3) support for Maintenance of Certification (MOC) to engage pediatricians in implementing the best practices.

[figure not shown]
**Aim 2:** Gather pilot data about the effectiveness of the intervention on clinician adherence to best practices and changes in practice capacity for change, adaptive reserve, and clinician self-efficacy.

**Aim 3:** Examine the congruence between documentation of the intervention in the EHR and youth report of the intervention.

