- a. Ask children about tobacco or nicotine product use
  - b. Ask parents or guardians about tobacco or nicotine product use
  - c. Ask children if they have quit smoking or stopped using nicotine products
  - d. Ask parents/guardians if they have quit smoking or stopped using nicotine products
  - e. Reinforce the importance of stopping tobacco or nicotine product use to the child
  - f. Reinforce the importance of stopping tobacco or nicotine product use to the parent/guardian
7. What do you feel are barriers to providing tobacco cessation interventions in pediatric primary care?  
(Response options: Strongly agree, Agree, No opinion or neutral, Disagree, Strongly disagree)
- a. Inability to get children to quit tobacco or nicotine product use
  - b. Inability to get parents/guardians to quit tobacco or nicotine product use
  - c. Lack of time for counseling or to set up a referral
  - d. No or limited provider reimbursement
  - e. Office layout is not conducive to private conversations with the child about tobacco and nicotine products
  - f. Child resistance to cessation treatment
  - g. Parent/guardian resistance to cessation treatment
  - h. Lack of training or experience in tobacco cessation interventions
  - i. Lack of available resources or referrals for pediatric cessation interventions
  - j. Lack of available resources or referrals for parent/guardian cessation interventions
8. Please provide your opinion/judgment for the following statements.  
(Response options: Strongly agree, Agree, No opinion or Neutral, Disagree, Strongly disagree)
- a. Tobacco and nicotine product cessation should be a standard part of pediatric primary care interventions for the child
  - b. Tobacco and nicotine product cessation should be a standard part of pediatric primary care interventions for the *parents/guardians*
  - c. I have had adequate training in tobacco and nicotine product cessation interventions
  - d. Clinicians need more training in tobacco and nicotine product assessment and cessation interventions
9. Have you smoked at least 100 cigarettes or used other tobacco products in your life?

- A. Yes
- B. No
- C. Don't know

10. Do you now smoke cigarettes or use other tobacco products every day, some days, or not at all?

- A. Every day
- B. Some days
- C. Not at all
- D. Not willing to answer

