## Appendix B. Adaptive Reserve and Change Process Capability Questionnaires

### B.1 Practice Structure

1. Approximately how often do the clinicians and staff at your practice site **hold meetings** to discuss the practice site's performance on:

*Check (✓) one for each of the following listed meeting topics:*

*(Response options: Never, Annually, Quarterly, Monthly, More often than monthly)*

- a. Overall pediatric quality of care?
- b. Patient satisfaction ratings?
- c. Productivity?
- d. Utilization or costs of care?
- e. Clinician or staff satisfaction?

2. Does your practice monitor the clinician(s) personal performance on ...

*(Response options: No, Yes, Don't know)*

- a. Overall pediatric quality of care
- b. Patient satisfaction ratings? (e.g., patient experience surveys)
- c. Productivity? (e.g., patient volume, procedure volume)
- d. Utilization or costs of care?

3. Does your practice monitor staff members' personal performance on...

*(Response options: No, Yes, Don't know)*

- a. Overall pediatric quality of care
- b. Patient satisfaction ratings? (e.g., patient experience surveys)
- c. Productivity? (e.g., patient volume, procedure volume)
- d. Utilization or costs of care?

4. Do the clinicians at your practice site use planned communications (e.g., letters, phone calls, text messages) to contact patients who are due for preventive care visits

*(Response options: No, Yes, Don't know)*

5. Does your practice site have:

*Check (✓) one for each of the following listed items:*

*(Response options: No, Yes, Don't know)*

- a. Agreements with community service agencies (e.g., health departments) to enhance services for any of your patients?
- b. A referral system for linking your patients to tobacco cessation programs

6. During a typical day in clinic, how often do providers use a computer or other electronic device (e.g., tablet, smart phone) to look up information about the patients they are seeing?

*Check (✓) one:*

- a. Never
- b. Rarely
- c. Sometimes
- d. Usually
- e. Always

7. Does your practice have an electronic medical record?
  - a. No
  - b. Yes
  
8. Does your site utilize an electronic medical record (EMR or electronic health record (EHR)?
  - a. Yes
  - b. No
  
9. If YES, please select the vendor of your practice's EHR:
  - a. Allscripts
  - b. CERNER
  - c. eClinicalWorks
  - d. eMD
  - e. EPIC
  - f. GE Healthcare Centricity
  - g. McKesson
  - h. NextGen
  - i. Practice Partner
  - j. Care360
  - k. Practice Fusion

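### The Adaptive Reserve short form cannot be identified in Appendix B, and no printed survey item covers the comfort part of clinician self-efficacy

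*Combined protocol and SAP*

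**What the plan says.** Aim 2 (section 5) covers pilot data on adherence and on "changes in practice capacity for change, adaptive reserve, and clinician self-efficacy". The Background (section 4) separates the two practice constructs as "ability to adopt new interventions (capacity for change) and sustain them (adaptive reserve"), and commits to measuring "clinician self-efficacy around the 6As at baseline and at 3 months post intervention".

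Section 6.2.3 B describes the instruments. In addition to the CPCQ, "Practices also will be asked to complete Adaptive Reserve Questionnaire (short form) at baseline and 9 months". The questions are said to assess two things: "physician self-efficacy (current practices, comfort with, beliefs about, and barriers toward tobacco screening and counseling"), and the organizational structure that supports new interventions. The Medical Director answers for the practice. The survey introduction before Appendix A confirms one Appendix B per practice, while Appendix A goes to each participating clinician. Section 6.2.3 A has the clinician survey completed at baseline and at 9 months.

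The appendix heading is "Appendix B. Adaptive Reserve and Change Process Capability Questionnaires". Its first part is "B.1 Practice Structure" and its second is B.2, the CPCQ. There is no third part. In section 6.2.5, the practice characteristics named for analysis are meeting frequency, performance evaluation and planned communication.

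**The concern.** The text on outcomes and the printed forms do not match. One promised questionnaire does not appear under its own name. The section on practice forms also assigns a clinician-level construct to a form that one person per practice completes.

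An item that is not asked at baseline cannot be recovered at 9 months. If the forms go out as printed, a later report of change in adaptive reserve would rest on practice structure, or on CPCQ items already used for capacity for change. A report of change in self-efficacy would rest largely on how often clinicians say they ask, advise and refer. That is close to adherence, which Aim 2 lists as a separate outcome.

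**Working it through.** The plan gives no figure to reproduce. The check is an item count of the printed forms against the constructs as the protocol itself defines them.

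**Adaptive reserve (Appendix B)**

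- B.1 has nine questions. Counted as response items: 5 (meetings) + 4 (clinician monitoring) + 4 (staff monitoring) + 1 (planned contact for preventive visits) + 2 (agency agreements, referral system) + 1 (computer use) + 3 (EHR use and vendor, Q7 to Q9) = 20.
- None of the 20 asks whether the practice can sustain an intervention, which is the Background's meaning of adaptive reserve. Four of them (Q6 to Q9) concern health IT, which the Background lists as a separate practice characteristic.
- B.2 has 9 + 12 = 21 items, all printed as CPCQ. Some, such as 1d (shared vision) and 1h (cohesive working environment), are close in content to adaptive reserve. None asks whether a past change was kept up.
- Items labelled Adaptive Reserve: 0 of 20 + 21 = 41.
- All three characteristics named in section 6.2.5 are B.1 topics (Q1, Q2 and Q3, Q4).

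**Clinician self-efficacy (Appendix A, against the four components in section 6.2.3 B)**

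| Component | Printed items | Count |
|---|---|---|
| Current practices | Q5 (13) + Q6 (6) | 19 |
| Barriers | Q7 | 10 |
| Beliefs | Q8a, Q8b, Q8d | 3 |
| Comfort | none | 0 |

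The total is 19 + 10 + 3 = 32 items on 3 of 4 components, answered by each clinician at both waves. The nearest items to comfort are Q8c, "I have had adequate training in tobacco and nicotine product cessation interventions", with Q7a (inability to get children to quit) and Q7h (lack of training or experience). The first and last concern training or experience and the other concerns an obstacle. None asks how comfortable or confident the clinician is.

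**Respondent**

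No item in Appendix B asks about a clinician's own practices, comfort, beliefs or barriers in tobacco counselling. The items that fit the stated definition are in Appendix A, so section 6.2.3 B points to the wrong form. Section 6.2.5 does not say which items make up self-efficacy, so the analysis plan does not settle the question.

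**The case against.** The best defence has three parts.

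First, the protocol defines self-efficacy broadly, and by that definition Appendix A measures most of it, repeatedly and per clinician. This stands. It leaves only comfort uncovered, together with the misplaced description in section 6.2.3 B.

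Second, B.1 may be the form that the authors mean. The appendix heading names two questionnaires and two parts are printed. Section 6.2.3 B says that the form covers organizational structure, and section 6.2.5 analyses B.1 topics under the two questionnaires' names. This is plausible and cannot be ruled out from the documents. Even so, B.1 would lack the self-efficacy content that the same paragraph ascribes to the form, and it does not ask about sustaining interventions.

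Third, section 6.2.3 B says that the CPCQ covers the capacity to sustain change, which overlaps the Background's definition of adaptive reserve. The overlap is real, so some related information is collected. But Aim 2 lists the two constructs separately, and one set of items cannot support two separate findings without a stated split.

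It is also possible that the short form exists and was simply not printed, since sites are told to complete it. The appendix does look unfinished: two B.2 items still refer to dental care and dentists, and B.1 Q7 and Q8 ask nearly the same thing. That is suggestive only.

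**Conclusion.** The concern holds in a limited form. The promised Adaptive Reserve short form is not identifiable among the 41 printed items of Appendix B. Comfort, one of the protocol's four components of self-efficacy, has no item in either appendix. Self-efficacy is also described as part of a form that does not contain it.

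A reader might infer that two of the three Aim 2 change outcomes are wholly unmeasured, that the surveys cannot show change in either, or that only the CPCQ is collected. The documents do not support this. Appendix A gives 32 repeated items on practices, barriers and beliefs, B.1 may be the intended organizational-structure part, and the CPCQ is said to reach sustaining change. Nor does the absence of some 6A steps from Q5 and Q6 add to the point: adherence is taken from record review, and Appendix E asks about readiness to quit and referral.

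The conclusion assumes that the printed appendices are complete. Some material just before the survey cover letter was not available for this check. Numbering runs without a gap (Appendix A Q1 to Q10, B.1 Q1 to Q9, then B.2), so lost items are unlikely but not excluded. These outcomes are secondary in a pilot, and the primary adherence outcome is unaffected. The change should still be made, because it affects what is collected or what may be concluded.

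**What to change.** Before baseline:

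1. Put the items of the named Adaptive Reserve short form into Appendix B, and report B.1 separately as practice structure. If B.1 is the intended form, say so and report it as organizational structure, not as adaptive reserve.
2. Add items on comfort with tobacco screening and counselling to Appendix A, identical at both waves. A few are enough; a new summed confidence scale is not needed.
3. Correct section 6.2.3 B so that clinician self-efficacy is taken from Appendix A and not from the Medical Director's form, and name the items that represent it.

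If no items are added, or baseline has already been collected, limit the Aim 2 conclusions to capacity for change, practice structure, and clinician-reported practices, beliefs and barriers.

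The cost is a slightly longer survey for clinicians and for the Medical Director, or a narrower Aim 2 claim.
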